## 1 List of Abbreviations

Abbreviations	Definitions
AB	Aunt Bertha
BMC	Boston Medical Center
BU	Boston University
BIDMC	Beth Israel Deaconess Medical Center
BWH	Brigham and Women's Hospital
BWFH	Brigham and Women's Faulkner Hospital
COC	Commission on Cancer
CTSI	Clinical and Translational Science Institutes
DFCI	Dana Farber Cancer Institute
DSMP	Data Safety Monitoring Plan
EHR	Electronic Health Record
HRSN	Health Related Social Need
MADPH	Massachusetts Department of Public Health
PN	Patient Navigator
SDOH	Social Determinants of Health
TRIP	Translating Research into Practice

## 2 Protocol Summary

Title:	Translating Research into Practice: TRIP
Population:	Newly diagnosed breast cancer patients 18 years or older who live within a 35 mile radius of Boston, MA and have any of the following risk factors for delays in care: are Black and/or Hispanic race/ethnicity, do not speak English as their primary language, and/or have only public insurance or are uninsured at the time of diagnosis.
Intervention:	Implementation of three evidence-based tools that facilitate timely treatment: (a) shared patient registry to identify and track patients from diagnosis through treatment; (b) systematic screening for SDOH with a web-based platform to support a personalized referral plan to regional resources; and (c) one-on-one patient navigation services. The integration of these tools into one integrated model of care will become the standard of care at each participating site, with the aim to improve the quality and timeliness of care delivery, for minority and/or low-income women with breast cancer.

---

Objectives:	The main study objective is to implement an evidence-based integrated care delivery model (patient registry, screening for social determinants of health (SDOH) and patient navigation) across six health systems in Boston and evaluate the impact on clinical care outcomes among minority, low-income women with breast cancer. The primary objective is to test the clinical effectiveness of the intervention, as measured by the time to first cancer treatment and receipt of guideline concordant care. The secondary objective is to evaluate the implementation of the intervention (fidelity to intervention protocol, local adoption/sustainability, and acceptability).
Design/Methodology:	We will conduct a stepped wedge hybrid effectiveness-implementation trial. The intervention proposed is a systems intervention. All subjects will be newly diagnosed breast oncology patients at one of the six participating clinical sites. In a stepped wedge design, sites are randomized to the time the site begins to implement the intervention and stratified by size. This will occur over an 18 month period, with a new site initiating the intervention every three months over this period. Historical data from each site serves as the comparison. Thus, 24 months prior to the time when the intervention begins at each site, women who meet the eligibility criteria will be given usual care (control) arm. Newly diagnosed cancer patients at the site after the time allocated to begin the intervention will be in the intervention arm. There will be no crossover.
Total Study Duration:	August 2018- July 2022
Subject Participation Duration:	Varies depending upon each patient's recommended cancer care as directed by their care team. Study participation will not influence the care recommended by the treatment team. Clinical outcomes will be collected from 0 to 24 months from the time of cancer diagnosis.

---

### 3 Background/Rationale & Purpose

#### 3.1 Background Information

In Boston (Massachusetts) inequities in breast cancer mortality have persisted and increased among Black, non-Hispanic women compared to women of other racial/ethnic groups. These inequities were reported in a national study of breast cancer mortality disparities in the 50 largest U.S. cities and confirmed in local, more current data from the City of Boston and Commonwealth of Massachusetts public health departments. From 1990-1994 to 2005-2009, the Black-White breast cancer mortality rate ratio in Boston increased from 0.94 to 1.49. Local data for the period 2007-2012 show a continuing Black-White mortality rate ratio of 1.36, as well as a Black-Hispanic mortality rate ratio of 4.60 and a Black-Asian mortality rate ratio of 5.28. From 2001-2012, this health inequity resulted in 74 excess Black deaths among women less than 65 years. The inequity is especially striking given that Black women in Boston receive mammography screening at the same rates, have approximately equal likelihood of presenting with advanced disease (4-5%), and had a lower incidence of breast cancer than White women

during this time period. Eliminating disparities requires evidence-based interventions that address barriers to care in communities at risk.

The transfer and application of scientific evidence into everyday practice is necessary to mitigate health disparities, yet roadblocks persist in broad implementation of evidence-based interventions among vulnerable communities experiencing disparities. The *Boston Breast Cancer Equity Coalition* was formed in 2014 in response to persistent city-wide disparities in breast cancer mortality among minority, low-income women. The *Coalition* identified three evidence-based strategies known to reduce delays in care that have yet to be deployed into clinical practice, due to a lack of implementation strategies.

**Translating Research into Practice (TRIP)** draws upon the principles of community-engaged dissemination and implementation science to systematically facilitate deployment and utilization of: (a) regional patient registries; (b) systematic screening for SDOH with a personalized referral plan; and (c) patient navigation services into one integrated model of care to improve the quality and effectiveness of care delivery, in this case for minority and/or low-income women with breast cancer. The four Massachusetts CTSA hubs (Boston University, Harvard University, Tufts University, and University of Massachusetts) partnered with the *Boston Breast Cancer Equity Coalition* to overcome barriers to widespread implementation and dissemination of evidence-based practices that will improve the delivery of guideline-concordant care to vulnerable women.

### **Research Question**

**The goal of this study is to overcome barriers to widespread implementation and dissemination of evidence-based practices that will improve the delivery of guideline-concordant care to vulnerable women.**

We plan to develop the three individual TRIP components (patient registry, systematic screening for SDOH using Aunt Bertha platform, patient navigation), and refine and integrate the intervention components into a cohesive package that can be implemented within the context of the clinical work flow of the partnering sites.

### **Hypothesis**

Our main hypothesis is that widespread implementation of these tools will eliminate care delivery disparities by reducing delays in time to first treatment. CTSA hubs have the translational expertise to overcome barriers to such implementation.

All participating sites currently provide patient navigation services, but none have evidence-based protocols, functional registries or social determinants of health platforms to support their patient navigation programs. As an integrated care delivery model, TRIP will benefit patients with breast cancer through individualized support and guidance. The only potential risk is a breach of confidentiality of data shared among the navigation network and the research team. This study will be conducted in compliance with the protocol, applicable regulatory requirements, and BMC/BU Medical Campus Human Research Protection policies and procedures.

### 3.2 Rationale and Purpose

The TRIP intervention addresses a critical gap in the research enterprise, namely the transfer and application of scientific evidence that is necessary to mitigate health disparities into everyday practice. TRIP includes an integrated, multi-component intervention that builds from preliminary work of the investigative team and their community partner, the Coalition. Using a community engaged approach, this study is designed to overcome barriers to widespread implementation and dissemination of evidence-based practices that will improve the delivery of guideline-concordant care to vulnerable populations. Innovations include: a collaborative community-driven approach, the regional patient registry, the Aunt Bertha Social Determinants of Health (SDOH) platform and the study design.

## 4 Objectives

### 4.1 Study Objectives

The main study objective is to conduct a stepped wedge hybrid effectiveness-implementation trial at six health systems (Beth Israel Deaconess Medical Center, Boston Medical Center, Brigham & Women's Faulkner Hospital, Dana-Farber Cancer Institute, Massachusetts General Hospital and Tufts Medical Center) in Boston caring for minority, non-English speaking and/or low-income women with breast cancer to assess clinical effectiveness and implementation of the integrated intervention (patient registry, Aunt Bertha SDOH platform, and patient navigation).

The primary objective is to test the clinical effectiveness of the intervention, as measured by the time to first cancer treatment and receipt of guideline concordant care. The secondary objective is to evaluate the implementation of the intervention (fidelity to intervention protocol).

### 4.2 Study Outcome Measures

#### 4.2.1 Primary Outcome Measures

Our primary study outcome is ***Time to initiation of cancer treatment***, a continuous outcome defined as the number of days from diagnosis (Time 0) to treatment initiation (Time 1). Treatment initiation is defined as the time from biopsy until first treatment for cancer, either surgical, radiation, or systemic therapy. **Table 2** displays the specific data elements that will be used to define treatment initiation. As some patients have had pre-operative chemotherapy or hormone therapy, the time period will vary for each patient. This outcome has been widely used in existing navigation studies, as it has been linked to mortality and survival outcomes. Our study is powered on this clinical effectiveness outcome.

**4.2.1.1 Table 1. Data Elements for “Time to Initiation of Primary Breast Cancer Treatment” Calculations**

Time period	Date of
Time 0	First definitive tissue diagnosis (i.e. biopsy)
Time 1a	First definitive surgical procedure (lumpectomy or mastectomy)
Time 1b	First external radiation therapy session
Time 1c	First chemotherapy infusion
Time 1d	First prescription for hormone therapy given

## 4.2.2 Secondary Outcome Measures

Secondary clinical outcomes include select measures of **Guideline Concordant or Quality cancer care**, as defined jointly by the Commission on Cancer and the National Comprehensive Cancer Network. Specific measures of guideline concordant/quality care (yes/no) are defined in **Table 3**. These measures of quality will allow us to monitor initiation and completion of specific types of cancer therapy (radiation, chemotherapy and hormonal therapy) for different subsets of women.

**4.2.2.1 Table 2. Secondary clinical outcomes: Guideline Concordant Care Quality Measures**

Treatment Domain	CoC* Criteria for Quality Cancer Care
Radiation	Radiation therapy administered within 365 days of diagnosis for women < 70 years receiving breast conserving surgery.
	Radiation therapy is recommended or administered following any mastectomy within 1 year (365 days) of diagnosis of breast cancer for women with $\geq 4$ positive regional lymph nodes.
Chemotherapy	Combination chemotherapy administered within 120 days of diagnosis for women <70 with AJCC T1c N0 M0, or Stage II or III ERA and PRA negative breast cancer. Completion of all planned chemotherapy cycles
Hormonal	Tamoxifen or third generation aromatase inhibitor administered within 365 days of diagnosis for women with AJCC T1c N0 M0, or Stage II or III ERA and/or PRA + breast cancer.

\*CoC=Commission on Cancer;  
<https://www.facs.org/quality%20programs/cancer/ncdb/qualitymeasures>

Outcomes that pertain to the implementation of the intervention in routine practice will be assessed through fidelity to the intervention protocol.

### Fidelity to Intervention Protocol

The assessment of intervention fidelity will utilize existing databases developed for the intervention components, protocol adherence monitoring reports, which will be reviewed at monthly in-person PI meetings (See Table 3). As part of their routine functions, navigators utilize these systems to track and monitor their activities and keep track of individual patients. Monthly aggregate reports using these databases will be generated for each navigator and reviewed by the study team. If a navigator does not achieve high levels of performance as determined by their adherence to navigation guidelines for the program, they will receive training buffer sessions as needed. If performance deficiencies are identified across navigators in specific areas, group meetings will be held to determine if protocol modifications are needed.

**4.2.2.2 Table 3. Implementation outcomes**

	Target	Data source	Time Period	Example Metrics
--	--------	-------------	-------------	-----------------

Fidelity to intervention protocol	Navigators	REDCap Registry	Monthly reports during intervention period	- adherence to the intervention protocol: (% elements on navigator protocol achieved, noted areas of deficiency)
	Navigators	Aunt Bertha Social Needs Screening platform	Monthly reports during intervention period	-adherence to the social determinants of health screening protocol: (% elements on navigator protocol achieved, noted areas of deficiency)

## 5 Study Design

### 5.1.1 Study design

We will conduct a randomized stepped wedge design. This pragmatic design involves a sequential, randomized roll-out of the intervention across 6 participating clinical sites over 3-month intervals or “steps”. Thus, each site receives the intervention. **Table 4** details this approach: 21-month full historical control period followed, sequential roll out of the intervention every 3 months over an 18-month period, then an additional 24 months of full study intervention. A 3-month wash-out period between the end of the historical control collection period and the beginning of the intervention roll-out period is designed to minimize subject crossover contamination. Subjects diagnosed with breast cancer during the washout periods will be excluded from analyses.

**5.1.1.1 Table 4. Stepped-wedge design of site rollout 2018-2019**

		21 Month Full Historical Control Period		Rollout Period			24-Month Full Intervention Period					Year 5 June – Sep 2021								
	Pre-TRIP	Year 1	Year 2	Year 3	Year 4	Year 5	Year 6	Year 7	Year 8	Year 9	Year 10									
	Sites	Historical Controls	Sept-Nov 2017	Dec 2017-Feb 2018	March-May 2018	June-Aug 2018	Sept-Nov 2018	Dec 2018-Feb 2019	March 2019	June – Aug 2019	Sept – Nov 2019	Dec 2019–Feb 2020	March – May 2020	June – Aug 2020	Sept – Nov 2020	Dec 2020–Feb 2021	March – May 2021			
1	Aug 2016 → May 2018			Wash-out (3M)	BW-Faulkner Hospital															
2	Aug 2016 → Jun 2018				Wash-out (3M)	Beth Israel Deaconess Medical Center														
3	Aug 2016 → Sep 2018					Wash-out (3M)	Tufts Medical Center													
4	Aug 2016 → Dec 2018						Wash-out (3M)	Boston Medical Center												
5	Aug 2016 → Mar 2019							Wash-out (3M)	Mass. General Hospital											
6	Aug 2016 → Jun 2019								Wash-out (3M)	Dana-Farber Cancer Institute										

### 5.1.2 Randomization scheme

Consistent with a stepped wedge design with one site implementing the intervention per step, prior to the collection of data in the pre-intervention period, a set of uniform random numbers has been generated for each of the six clusters to assign a starting period for the study intervention. There will be no crossover of patients from usual care to the intervention. That is, patients at each site during the pre-intervention period will experience only usual care and those enrolled after the initiation of intervention will experience the intervention.

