## 5.1.6 Data Sources/Collection

**(1) The Electronic Health Records (EHR) will serve as the data source for all socio-demographic and clinical covariates, as well as the primary and secondary clinical effectiveness outcomes for historical controls and intervention subjects. At Boston Medical Center the EHR will also be used to source social needs screening data from a parallel instance of Aunt Bertha called THRIVE. The THRIVE SDOH for TRIP patients will be retrieved from BUMC's Clinical Data Warehouse (CDW) and merged with the social needs screening data from the TRIP instance of Aunt Bertha by the TRIP analyst. The clinical and demographic EHR data from the 6 sites will be used in two ways: 1) to create a *potential patient list* to aid Patient Navigators in identifying potentially eligible patients with new breast cancer diagnoses (these data will be kept at the clinical site) and 2) treatment data needed for TRIP analysis (i.e., Chemotherapy regimens)**

Treatment variables will be *manually abstracted* for both historical controls and enrolled intervention subjects. Abstraction into a HIPAA compliant REDCap form will be completed by trained study personnel 16-18 months after diagnosis to ensure complete treatment information is documented through the 12 months following diagnosis. The electronic health records will also be used to obtain patient contact information (mailing address and phone number) for patient interviews assessing patient acceptability of the intervention.

- (2) **The REDCap registry and SDOH screening platforms (Aunt Bertha, THRIVE, QuickBase)** are the main sources of implementation (Fidelity) data. Each will provide measures of fidelity to the intervention protocol. Navigators utilize these systems to track and monitor their activities related to individual patients. Monthly aggregate reports will be generated for each navigator, reviewed by the study team and used for performance improvement throughout the study. Fidelity metrics include categorical assessments of navigator use of these tools, and will be linked to outcomes. The REDCap registry and SDOH screening platforms will also be used to identify navigated patients for patient acceptability interviews. Only patients who have been contacted by a TRIP patient navigator and screened for social determinants of health will be contacted for participation in interviews.

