# **7 Study Subject Selection**

## **7.1 Subject Inclusion Criteria**

In order to be eligible to participate in this study, an individual must meet all of the following criteria:

Eligibility criteria: All women with breast cancer diagnosed during the study period will be eligible for inclusion if they meet three study criteria:

1. are an adult female 18 years of age or older;
2. reside within a 35 mile radius of Boston;
3. have any of the following risk factors for delays in care:
  - a. Black and/or Hispanic race/ethnicity
  - b. do not speak English as their primary language and/or
  - c. have only public insurance or are uninsured at the time of diagnosis.

Women who do not meet all three criteria will be excluded from the study. In some cases it is possible, due to the scope of the patient navigator's responsibilities that patients who are ineligible will be entered into the Registry. As the registry is HIPAA compliant and these individuals will be excluded from compiled data sets, the study team does not perceive this to be a major risk.

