#### **9.3.4 Patient Identification**

Navigators will identify patients in 2 ways: 1) using their standard methods as part of their clinical workflow. The majority of patients will be identified via physician or social worker referral at the clinical site of origin, or through discussion of the case in the Breast Cancer tumor board or case conference. 2) using a potential patient list provided by their site's IT/Research Administration to review patients that match eligibility criteria prior to an upcoming scheduled oncology appointment.

As part of the TRIP intervention, patient navigators at each of the 6 clinical sites are responsible for identifying eligible patients based on the aforementioned eligibility criteria. In order to facilitate effective identification of eligible patients as part of each navigator's workflow, the TRIP

team is collaborating with Information Technology personnel at each clinical site to produce a potential patient report. At each individual site, these reports will be generated weekly from electronic medical records and produce a list of patients who meet the following criteria:

1. A scheduled visit for a diagnosis of breast cancer in the next one to two weeks
2. A ZIP code within a 35 mile radius of Boston
3. Other key eligibility criteria (non-white, non-English speaking, and/or uninsured/public insurance)

The PHI data included in these reports are patient name, MRN, appointment type, provider, race/ethnicity, primary language, ZIP code, and insurance (if available). These reports are unique to each site and are accessible locally via secure folder or encrypted email by a patient navigator and in some cases, study team personnel at their site.

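### Intervention-arm membership is described by diagnosis in one place and by enrolment in another, and no rule classifies women for whom the two disagree

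*Combined protocol and SAP*

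**What the plan says.** The Protocol Summary (Design/Methodology) states: "Newly diagnosed cancer patients at the site after the time allocated to begin the intervention will be in the intervention arm". The anchor is a new diagnosis, measured against the allocated time.

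Section 5.1.2 first says "There will be no crossover of patients from usual care to the intervention". It then explains that patients at a site in the pre-intervention period receive usual care only, and that "those enrolled after the initiation of intervention will experience the intervention". The anchor here is enrolment.

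Other sections bear on who ends up in each group:

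- Section 5.1.1 keys the wash-out to diagnosis: "Subjects diagnosed with breast cancer during the washout periods will be excluded from analyses".
- Section 7.1 sets the eligibility window: "All women with breast cancer diagnosed during the study period will be eligible for inclusion if they meet three study criteria". It does not refer to the site's start date, and 7.2 lists no exclusions.
- Section 9.3.4 gives the first criterion for the weekly list as "A scheduled visit for a diagnosis of breast cancer in the next one to two weeks". No limit on diagnosis date is listed.
- Section 5.1.6 has treatment data abstracted "for both historical controls and enrolled intervention subjects".
- Section 10.1.5 takes controls from each site's tumor registrar, by historical period.
- Section 12.3 adopts intent-to-treat without saying what date or event places a woman in a group.

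**The concern.** Group membership defines the primary comparison. Here the control group is fixed by a registry and a date, while the intervention group depends on being found and enrolled by staff who know the go-live date and deliver the programme. Two kinds of error are left open.

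**Control-period outcomes in the intervention arm.** A woman diagnosed before the wash-out and still attending visits after go-live could be enrolled and counted as intervention. Her time to first treatment would usually have been settled under usual care, so the effect would be diluted. She would also remain on the registrar's list.

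**Missing intervention-period women.** An eligible woman diagnosed after the start but never enrolled belongs to the intervention arm under the Summary, yet 5.1.6 provides no chart abstraction for her. If such women are harder to reach and start treatment later, leaving them out would flatter the intervention. The registrar-based control list makes no matching omission.

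**Working it through.** **Step 1. Apply the texts to specific women.**

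| Woman | Summary | Section 5.1.2 | Data source |
|---|---|---|---|
| Diagnosed before the wash-out, first enrolled after the start, same site | Not intervention | First half of the sentence points to usual care, second half to intervention | Registrar's list and enrolled list |
| Diagnosed at a site not yet live, transfers to a live site and is enrolled there | Unclear which site's start governs | Intervention, by enrolment | Registrar's list at the diagnosing site and enrolled list at the second site |
| Diagnosed during the wash-out | Not addressed | Not addressed | Excluded by 5.1.1 |
| Eligible, diagnosed after the start, never enrolled | Intervention | Silent | Not abstracted under 5.1.6 |

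Only the third row is settled. The second row is not far-fetched: 9.3.1 and 9.3.6 put care at more than one institution, or transfer, at 20% of patients. Section 10.1.5 identifies multi-institution controls by a registry match but gives no rule for classifying them.

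**Step 2. The plan's own sample size.** Section 12.2 has 220 per group and a design effect of 2.29: 220 × 2 × 2.29 = 1,007.6, which rounds up to the stated 1,008. The planned total is 1,300 (633 control, 667 intervention).

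**Step 3. How many women could be affected.** In Table 6, control/total × 60 months gives:

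- BWFH: 58/166 × 60 = 21.0
- BIDMC: 85/213 × 60 = 23.9
- Tufts: 32/71 × 60 = 27.0
- BMC: 224/448 × 60 = 30.0
- MGH: 78/142 × 60 = 33.0
- Brigham/DFCI: 156/260 × 60 = 36.0

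These fit three-month steps within a 60-month window per site, so accrual is 1,300/60 = 21.67 a month. Women diagnosed 3 to 12 months before their site's go-live lie outside the wash-out and within a year of diagnosis: 9 × 21.67 = 195, or 195/633 = 30.8% of controls.

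**Step 4. Effect on power.** Let f be the share of the 195 enrolled after go-live. The documents give no value for f. Assume these women have the usual-care proportion of 70% and that all 633 women stay on the control side.

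- Intervention n = 667 + 195f
- Diluted share d = 195f/n
- Observed intervention proportion p = 0.81 − 0.11d
- SE = √[0.70 × 0.30/(633/2.29) + p(1 − p)/(n/2.29)]
- Power = Φ[(p − 0.70)/SE − 1.96]

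| f | n | d | p − 0.70 | SE | Power |
|---|---|---|---|---|---|
| 0 | 667 | 0% | 0.1100 | 0.0359 | 86.5% |
| 0.25 | 715.75 | 6.8% | 0.1025 | 0.0356 | 82.1% |
| 0.5 | 764.5 | 12.8% | 0.0960 | 0.0353 | 77.6% |
| 1 | 862 | 22.6% | 0.0851 | 0.0348 | 68.8% |

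**Step 5. Women still untreated at go-live.** Assume exponential times with 70% treated by t days, a daily rate of 21.67/30.4 = 0.713, λ = −ln(0.30)/t, and a wash-out of 91 days. The expected number diagnosed before the wash-out and still waiting is 0.713 × 0.30^(91/t)/λ. This gives about 2, 6 or 16 women for t = 45, 60 or 90 days. Most of the 195 would therefore already have started treatment.

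**The case against.** The strongest reply is that the plan clearly means to recruit at diagnosis. Section 5.1.4 asks for a new diagnosis, 9.1 aims for navigation to begin within 7 days of it, 5.1.5 expects every eligible woman to be enrolled, and crossover is ruled out in both the Summary and 5.1.2. Section 7.1 also says that ineligible women entered in the registry are removed from compiled data. On that reading f is near zero and the effect negligible. This stands as a reason to expect a small problem. It does not supply a rule: new is undefined, the 7 days is an aim, and 7.1 treats diagnosis in the control years as eligible.

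Three stronger readings are tempting but not supported:

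- A reader might infer that navigators decide the arm. They can affect who is found and enrolled, but controls are set by the registrar's list and navigators cannot take a woman off it.
- A reader might take 5.1.2 as an allocation rule based on the actual start, in breach of intent-to-treat. The text says only initiation, which may mean the assigned start. The sentence describes the care experienced, following a no-crossover statement, and no off-schedule start is documented.
- A reader might set the 80% power point at 1,300 women and so find a steeper loss. Section 12.2 reaches 80% at 1,008.

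**Conclusion.** The inconsistency is real: the anchors differ between the Summary, 5.1.2 and 5.1.6, and women for whom they disagree have no stated arm. The consequence is uncertain and probably small. At f = 0.25 power stays above the planned 80%; at f = 0.5 it falls slightly below; only near-complete enrolment of earlier-diagnosed women brings it to about 69%, which sits poorly with recruitment near diagnosis.

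These figures rest on the assumed f, the 60-month window inferred from Table 6, a 70% proportion among the misplaced women, the stated design effect taken at face value, and a simple two-proportion comparison. They also keep double-listed women among the controls; moving them out would cost somewhat more power. The effect of omitting unenrolled women is not quantified, because the documents give no figure for them. The case for acting is that the arm definition should not be left to enrolment practice or to the analysis stage.

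**What to change.** In 5.1.2, and in matching words in the Summary, 7.1 and 12.3, state:

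- The analyst assigns study arm from Time 0 (defined in the data-element table at 4.2.1.1) relative to the randomised start date of the diagnosing site.
- Time 0 before the wash-out is control, during it is excluded, and on or after the start is intervention, regardless of whether or when a navigator enrols the woman.
- Each woman is counted once, including those seen at more than one site.
- If a site starts off schedule, an as-implemented sensitivity analysis is reported.

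Change 5.1.6 so that abstraction covers all eligible women in the intervention period. Taking them from the registrar source already used for controls would make the two groups comparable in how they are found. While editing the Summary, reconcile its control window, "24 months prior to the time when the intervention begins at each site", with the 21-month period and wash-out in 5.1.1.

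The cost is modest. The diagnosis date is already collected, so the rule itself needs only wording. A few enrolled women leave the intervention count, and some unenrolled eligible women need chart abstraction.
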